8.6.1 Definition of Treatment Emergent Adverse Event (TEAE)

Adverse Events (AEs) are any untoward medical occurrence, unintended disease or injury, or untoward clinical signs (including abnormal laboratory findings) in subjects, whether or not related to the investigational medical device and whether anticipated or unanticipated. TEAEs are adverse events (AEs) that either start after initial treatment, or which are present prior to treatment initiation but which increase in severity after treatment. No AEs that are not TEAEs are expected in this study since the time between enrollment and first treatment is very brief.

Any medical condition that is present at the time that the subject is screened will be captured as part of the study subject's baseline medical history and will serve as the basis for capturing AEs that are treatment-emergent based on worsening severity.

TEAEs can be further divided into solicited TEAEs and unsolicited TEAEs. Solicited TEAEs are those for which the study team will specifically query the subject whether they occurred. Unsolicited TEAEs are those events that the subject report occurring without being queried about the specific event.

All TEAEs will be assessed for severity and relationship to study intervention/investigational device. Reporting of all TEAEs, solicited and unsolicited, will occur during the period from study device administration on Day 1 through Day 14 or until an early termination visit.

All TEAEs, solicited and unsolicited, will be captured on the appropriate source documents and e-CRFs. Information to be collected for TEAEs includes event description, date of onset, assessment of severity, relationship to study product and alternate etiology (assessed only by those with the training and authority to make a diagnosis such as the participating clinical site PI or appropriate sub-investigator), date of resolution, seriousness, and outcome. All TEAEs will be documented regardless of relationship.

TEAEs will be followed to resolution or stabilization.

8.6.2 Solicited Treatment Emergent Adverse Events – Reactogenicity

Solicited TEAEs are anticipated TEAEs for which consistent collection of information is desired. Study clinicians will follow and collect resolution information for any reactogenicity symptoms that are not resolved during the active study period.

Solicited TEAEs (i.e., reactogenicity) will be collected by direct questioning of study subjects and recorded on the appropriate source document and e-CRF during the entire course of the study.

For this study, solicited TEAEs include:

- Illumination site Pain
- Illumination site Erythema
- Illumination site Edema/Induration
- Any other pain, redness, swelling or lesion of the oral mucosa

	Page 47 of 70
EmitBio Inc.	Version: 3.1
EB-P30-01	7 February 2024

8.6.3 Unsolicited Treatment Emergent Adverse Events

All TEAEs spontaneously reported by the subject and/or in response to an open question from study staff or revealed by observation, physical examination or other diagnostic procedures must be recorded on the appropriate source document and e-CRF.

Unsolicited AEs of all severities will be reported during the entire course of the study.

8.6.4 Treatment Emergent Adverse Event Reporting

Information on all TEAEs should be recorded on the appropriate source document and e-CRF. All clearly related signs, symptoms and results of diagnostic procedures performed because of an TEAE should be grouped together and recorded as a single diagnosis.

8.6.5 Definition of a Serious Adverse Event (SAE)

An SAE is defined in 21 CFR 312.32 as follows: "An AE is considered serious if, in the view of either the participating clinical site PI or appropriate sub-investigator or the sponsor, it results in any of the following outcomes:

- Death,
- A life-threatening adverse event,
- Inpatient hospitalization or prolongation of existing hospitalization,
- A persistent or significant incapacity or substantial disruption of the ability to conduct normal life functions, or
- A congenital anomaly or birth defect.

Important medical events that may not result in death, are not immediately life-threatening, or require hospitalization may be considered serious when, based upon appropriate medical judgment, they may jeopardize the subject and may require medical or surgical intervention to prevent one of the outcomes listed in this definition. An example of such a medical event would be an allergic bronchospasm requiring intensive treatment in an emergency room or at home to prevent the development of one of the definitions above.

"Life-threatening" refers to an AE that at occurrence represents an immediate risk of death to a subject. It does not include an adverse event or suspected adverse reaction that, had it occurred in more severe form, might cause death. Similarly, a hospital admission for an elective procedure is not considered an SAE.

All SAEs will be assessed for severity and relationship to study intervention. All SAEs will be recorded on the appropriate SAE e-CRF.

	Page 48 of 70
EmitBio Inc.	Version: 3.1
EB-P30-01	7 February 2024

All SAEs will be followed through resolution or stabilization by a study clinician, licensed to make medical diagnoses and listed as the participating clinical site PI or appropriate sub-investigator.

All SAEs will be reviewed and evaluated by the Sponsor and will be reported according to the Reporting Requirements. This report will include severity, association with the study device, action(s) taken, and outcome.

8.6.6 Serious Adverse Event Reporting

Any TEAE that meets a protocol-defined criterian as an SAE must be reported immediately (within 24 hours of site awareness) using the electronic data collection tool, eCRF. Investigators must report all Safety Events (AEs, SAEs and Device Deficiencies) via the Electronic Data Capture (EDC) system. If the electronic system is unavailable, then the site will use the paper SAE data collection tool to report the event within 24 hours and send to the IQVIA MedTech Safety management team by email: [contact].

Other supporting documentation of the event may be requested by EmitBio's Medical Monitor and should be provided as soon as possible. The Sponsor Medical Monitor will review and assess the SAE for regulatory reporting and potential impact on study subject safety and protocol conduct.

At any time after completion of the study, if the participating clinical site PI or appropriate subinvestigator becomes aware of an SAE that is suspected to be related to study product, the participating clinical site PI or appropriate sub-investigator will report the event to the U.S Food and Drug Administration using MedWatch, FDA's Safety Information and Adverse Event Reporting Program.

8.6.7 Regulatory Reporting of Device-related AEs

EmitBio Inc. will report to the FDA any unanticipated device-related TEAEs and SAEs as soon as possible, but in no case later than 10 working days after the sponsor's initial receipt of the information.

Relevant follow-up information to the safety report will be submitted as soon as the information is available. Upon request from FDA, EmitBio will submit to the FDA any additional data or information that the agency deems necessary.

SAEs that are not considered related to RD-X19 will not be reported to the FDA.

8.6.8 Classification of a Treatment Emergent Adverse Event

The determination of seriousness, and causality will be made by an on-site investigator who is qualified (licensed) to diagnose TEAE information, provide a medical evaluation of TEAEs and classify TEAEs based upon medical judgment. This includes, but is not limited to, physicians, physician assistants and nurse practitioners.

	Page 49 of 70
EmitBio Inc.	Version: 3.1
EB-P30-01	7 February 2024

8.6.9 Severity of Treatment Emergent Adverse Events

All TEAEs will be assessed for severity according to the toxicity grading scale of mild, moderate, and severe..

The following guidelines will be used to describe severity:

- Mild (Grade 1): Events that are usually transient and may require only minimal or no treatment or therapeutic intervention and generally do not interfere with the subject's usual activities of daily living.
- Moderate (Grade 2): Events that are usually alleviated with additional specific therapeutic intervention. The event interferes with usual activities of daily living, causing discomfort but poses no significant or permanent risk of harm to the research subject.
- Severe (Grade 3): Events interrupt usual activities of daily living, or significantly affects clinical status, or may require intensive therapeutic intervention. Severe events are usually incapacitating.

TEAEs characterized as intermittent require documentation of onset and duration of each episode. A TEAE is not counted as a separate or new TEAE if at the next clinic visit, the TEAE is persistent at the same of lesser severity level. It shall be recorded as a new TEAE if it worsens in severity. The same TEAE verbatim term with a worsened severity score will be documented as an independent event, including start and stop dates. The start and stop date of each reported TEAE will be recorded on the appropriate e-CRF. All device-related grade ≥ 2 TEAEs (any grade greater than mild is considered unanticipated) will be reported.

See SAE source document for information to be submitted.

8.6.10 Relationship to Study Intervention/Investigational Device

For each reported adverse event, the participating clinical site PI or qualified designee must assess the relationship of the event to the study device using the following guidelines:

- Related The AE is known to occur with the study intervention, there is a reasonable possibility that the study intervention caused the AE, or there is a close temporal relationship between the study intervention and event. Reasonable possibility means that there is evidence to suggest a causal relationship between the study intervention and the AE.
- Not Related There is not a reasonable possibility that the administration of the study intervention caused the event, there is no temporal relationship between the study intervention and event onset, or an alternate etiology has been established.

	Page 50 of 70
EmitBio Inc.	Version: 3.1
EB-P30-01	7 February 2024

8.6.11 Time Period and Frequency for Event Assessment and Follow-Up

Solicited and Unsolicited TEAEs will be recorded by clinical trial staff for the entire duration of the study, beginning after device administration and through day 14 (\pm 2 days) or an early termination visit.

8.6.12 Treatment Emergent Adverse Event Reporting to Study Subjects

The Sponsor will ensure all device-attributed TEAEs and SAEs are reported to participants in the study to better inform them of the potential risks vs. benefits of participation.

8.7 Reporting Summary

Report	Time to Report	Responsibility	Report To
Unanticipated (in terms of nature, severity (≥ 2), or degree of incidence) Adverse Device-Related Event including Serious Unanticipated Adverse Device Events [21 CFR 812.150]	Within 10 working days after becoming aware	Investigator	CRO/Sponsor IRB
Unanticipated Adverse Device-Related Event including Serious Unanticipated Adverse Device-Related Events – Results of Evaluation [21 CFR 812 150]	Within 10 working days after becoming aware File as an IDE report to FDA	Sponsor	FDA IRBs, all Investigators, all
TEAE - unsolicited	Within 24 hours of becoming aware	DCT	Investigator
SAEs or TEAEs that are unanticipated, including a change in severity (≥ 2), and are treatment/device related	Within 10 working days after becoming aware	Investigator	CRO/Sponsor IRB
SAEs or TEAEs that are unanticipated, including a change in severity (≥ 2), and are treatment/device related	Within 10 working days after becoming aware File as an IDE report to FDA	Sponsor	FDA IRBs, all Investigators, all
Use of Investigational Device Without Informed Consent [21 CFR 812.150]	Within 5 working days of the device use	Investigator	CRO/Sponsor IRB

EmitBio Inc. EB-P30-01

Use of Investigational Device Without Informed Consent [21 CFR 812.150]	Within 5 working days of becoming aware	Sponsor	FDA
Unapproved protocol deviations/violations (an accidental or unintentional change to the IRB-approved protocol) – Major Deviation	Within 10 business days from the time of identification of the unplanned or unintentional protocol deviation/violation	Investigator	IRB
Deviations from the investigational plan to protect the life or physical well-being of a subject in an emergency. [21 CFR 812.150]	Within 5 working days of the emergency	Investigator	IRB CRO/Sponsor

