EmitBio has implemented a Risk Management process that is compliant with ANSI AAMI ISO 14971:2019 and, with the guidance of ISO/RT 24971:2020, developed a Risk Management Plan specifically for the RD-X19 system. Risk Management activities have been conducted in accordance with to the Risk Management Plan and internal Standard Operating procedures, including a Hazards Analyis to identify characteristics of the RD-X19 device that could affect safety and separate risk analyses that focus on the design and use/misuse related hazards.

The Sponsor intends to continue development of RD-X19 as a NSR device and conduct this clinical study without an Investigational Device Exemption (IDE) application approved by FDA prior to initiation.

Strict safety oversight will provide rapid detection of significant device-related TEAEs warranting pausing or halting the trial. See Section 8.5, Safety and Other Assessments, for detailed description of study Pausing and Stopping Rules.

7.1.2 Proposed Label Claim/Indication for Use:

The EmitBio RD-X19 device is intended for use as a treatment for mild COVID-19 in subjects with positive results of direct SARS-CoV-2 viral testing ages 40 years of age and older who are symptomatic for 72 hours or less.

7.1.3 Medical Device Quality System:

EmitBio will operate under an established Quality Management System (QMS), with a commitment for continuous improvement and effectiveness, in accordance with the requirements of the customers and applicable international standards. Specifically, the EmitBio Quality Management System is compliant with the requirements of the FDA Quality Systems Regulations (QSR). Any device that malfunctions during the trial will be fully evaluated and documented in compliance with EmitBio's QMS.

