7.5 Device Discontinuation

7.5.1 Study Pausing Criteria

If observations of any potential device-related SAE or patterns of non-resolving device-related TEAEs with severity grade 2 or higher in the same System Organ Classification Preferred Term (SOC PT) are observed in a single subject, treatment will be discontinued for that subject and they will continue with the full study schedule including collection of all data as if they had continued to be treated.

EB-P30-01 enrollment may be paused if any of the following events occur:

- Any subject experiences a device-related SAE.
- Any subject experiences laryngospasm, bronchospasm, or anaphylaxis within 2 hours after treatment.
- Two (2) or more subjects experience an allergic reaction such as generalized urticaria (defined as occurring at three or more body parts) within 72 hours after treatment.
 - Potential photo-allergy or phototoxicity to one or more photosensitizing drugs in the subject's medical history should be investigated in all cases. See "Medications that Increase Sensitivity to Light: A 1990 Listing (Levine 1990)."
- Three (3) or more subjects experience a Grade 2 or higher TEAE within the same SOC PT based on the Medical Dictionary for Regulatory Activities (MedDRA) coding, considered to be related to RD-X19.

While the study is paused, a complete review of safety findings will be performed by an Independent Medical Monitor at the earliest opportunity and will make a recommendation to the Sponsor regarding continuation or termination of all or some of the study subjects and/or the overall study protocol. The Independent Medical Monitor has no affiliation with the design or conduct of the trial. The recommendation will be taken under advisement by the study Sponsor who has responsibility for any final decision.

A study volunteer may elect to discontinue participation in the trial at any time. Investigative staff will ask the volunteer to return for an early termination evaluation, but they are under no obligation to do so. All study subjects must return the RD-X19 device at study termination and

	Page 34 of 70
EmitBio Inc.	Version: 3.1
EB-P30-01	7 February 2024

study staff must verify that the device serial number matches the study subject to whom it was assigned.

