7.5.2 Study Stopping Criteria

If ≥ 2 device-related SAEs or ≥ 3 device-related severe TEAEs (grade 3) in the same SOC PT are observed, further enrollment and treatment will be discontinued. Subjects on trial at the time on discontinuation will continue to be followed per protocol.

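### Non-serious device-related TEAEs of Grade 2 or higher count toward the pausing trigger, and Grade 3 ones toward the stopping trigger, but the only stated limit for reporting them to the sponsor is 10 working days

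*Protocol*

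**What the plan says.** Protocol 7.5.1 introduces its list with "EB-P30-01 enrollment may be paused if any of the following events occur". One item is "Three (3) or more subjects experience a Grade 2 or higher TEAE within the same SOC PT", restricted to events considered related to the device. Protocol 7.5.2 is firmer: "If ≥ 2 device-related SAEs or ≥ 3 device-related severe TEAEs (grade 3) in the same SOC PT are observed", both further enrollment and treatment end.

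Protocol 8.6.9 settles how such events are classed: "All device-related grade ≥ 2 TEAEs (any grade greater than mild is considered unanticipated) will be reported". They therefore fall in the 8.7 row for "SAEs or TEAEs that are unanticipated, including a change in severity (≥ 2), and are treatment/device related". In that row the investigator reports to the CRO/Sponsor and the IRB, with a limit of 10 working days from awareness.

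Protocol 8.6.6 sets a shorter limit for serious events. An SAE "must be reported immediately (within 24 hours of site awareness) using the electronic data collection tool, eCRF". The same section sends all other adverse events through EDC but gives no time limit for them. For a suspected related SAE that the site learns of after completion of the study, the investigator "will report the event to the U.S Food and Drug Administration using MedWatch"; neither the sponsor nor the IRB is mentioned.

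Protocol 7.1.1 states the purpose of the oversight: "Strict safety oversight will provide rapid detection of significant device-related TEAEs warranting pausing or halting the trial".

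**The concern.** The TEAE triggers are counts over subjects in the whole trial. Protocol 6.2.1 caps each site at 15% of randomized subjects, so there must be at least seven sites (1/0.15 = 6.7), and SAP 8.2.6 lists sites in 21 states. Three qualifying events can easily fall at three different sites, where no single investigator can see that the threshold has been met. Independent Medical Monitor review does not fill the gap, because it starts during a pause or on referral from the sponsor and so depends on the sponsor already knowing.

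The rules can act no sooner than the reports arrive. If a fully compliant site may hold a qualifying report longer than a treatment course lasts, the reporting limits do not deliver what 7.1.1 says the oversight will provide.

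**Working it through.** No power, alpha or sample size figure is involved, so the plan has no figure of its own to reproduce. The check sets the triggers beside the reporting limits and then converts the limit to calendar days.

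**Step 1. Which site-to-sponsor limit applies to which trigger.**

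| Event | Rule it feeds | Stated limit to the sponsor |
|---|---|---|
| Non-serious, device-related, Grade 2 | Pausing (7.5.1) | 10 working days (8.7, via 8.6.9) |
| Non-serious, device-related, Grade 3 | Pausing and stopping (7.5.1, 7.5.2) | 10 working days (8.7, via 8.6.9) |
| Device-related SAE | Pausing at one, stopping at two | 24 hours (8.6.6); also 10 working days if unanticipated (8.7) |

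The other 24-hour line for TEAEs in 8.7 runs from the decentralized team to the investigator, so it does not shorten the route to the sponsor.

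**Step 2. Ten working days in calendar days** (weekends excluded, no public holidays).

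- Not counting the day of awareness: 14 days if the site becomes aware Monday to Friday, 13 on a Saturday, 12 on a Sunday. Range 12 to 14.
- Counting a working day of awareness as day 1: 11 days for Monday, 13 for Tuesday to Friday, and still 13 and 12 for the weekend. Range 11 to 13.
- Public holidays lengthen either count.

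**Step 3. Compare with the treatment course.** Treatment lasts 7 consecutive days (4.2), with the last treatment on Day 8 under the split schedule (8.3.1). Even the shortest count, 11 days, is longer. Every subject on treatment when a site becomes aware can finish all 14 treatments before the report is due. An event known to the site on Day 1 need not reach the sponsor until about Day 12 to 15, around or after the Day 14 visit.

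**Step 4. Subjects who could enter in the interval (illustration only).** The documents do not state an accrual rate. If 326 subjects accrued over 6 to 12 months:

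- 12 months: 326/52 = 6.3 per week, about 13 in two weeks.
- 6 months: 326/26 = 12.5 per week, about 25 in two weeks.

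Half would be on the active device. The comparison in Step 3 does not need this assumption.

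**Step 5. SAEs.** For an unanticipated device-related SAE, 8.6.6 and 8.7 name the same reporter and the same destination with different limits, and the 8.7 table has no 24-hour SAE line. A site that meets 24 hours meets both. A site working only from the table could take 10 working days and believe it had complied.

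**Step 6. Late SAEs.** Section 8.6.6 does not say whether completion of the study means the subject's completion or the trial's. If the trial's, the pausing and stopping rules no longer matter by then. If the subject's, a related SAE could occur while others are still enrolling, and this sentence does not direct it to the sponsor. Section 8.6.7 starts the sponsor's FDA clock at the sponsor's own receipt of the information, so sponsor receipt matters there too.

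**The case against.** The strongest reply is that the two-week lag is a ceiling. All adverse events go into EDC (8.6.6), subject data are quality-checked daily (7.4), televisit reports are uploaded within 24 hours (10.5), the sponsor's Medical Monitor reviews safety regularly (4.3), and patterns of device-related TEAEs are to be referred at once to the Independent Medical Monitor (4.3). All of this is true and makes a full two-week delay unlikely. However, none of it sets a time limit for a graded, device-attributed TEAE to travel from site to sponsor.

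Several stronger readings are tempting, and the documents do not support them:

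- That Grade 2 events drive the stopping rule. They feed only the pausing list, which is discretionary; 7.5.2 requires Grade 3 TEAEs or SAEs.
- That faster reporting under the pausing rule would spare subjects already on treatment. The pause acts on enrollment; only 7.5.2 expressly ends treatment across the trial. The affected subject is covered separately, because 7.5.1 discontinues treatment in an individual with a related SAE or a pattern of non-resolving related events of Grade 2 or higher, without any cross-site count.
- That every trigger needs a sponsor tally. One related SAE is a single-subject pausing trigger.
- That the two SAE limits exclude each other. They overlap, and delay arises only if the 24-hour rule is not followed.
- That late SAEs are withheld from the sponsor. This reads intent into silence; the 8.7 rows are not limited to on-study events.
- That the non-significant-risk case rests on rapid detection. Section 7.1.1 argues it from the regulatory criteria and the risk review; the sentence on oversight comes after that decision.

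**Conclusion.** The point holds for non-serious device-related TEAEs of Grade 2 or higher. They count toward a pausing trigger and, at Grade 3, toward the stopping trigger, yet the only stated limit for reporting them to the sponsor is 10 working days. That is 12 to 14 calendar days (11 to 13 if the day of awareness counts), against a 7-day course. Within those limits a threshold can be crossed across sites while enrollment continues and, where the stopping rule is concerned, while treatment continues. This is the maximum the protocol permits, not a forecast. The figure of 13 to 25 further subjects depends on an assumed accrual period and on the full lag being used.

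The SAE and late-SAE points are smaller and separate. The first is an overlap between 8.6.6 and 8.7 that could mislead a site using the table alone. The second is an undefined term and an unnamed recipient. Neither is needed for the timing conclusion. Nothing here touches the efficacy analysis.

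**What to change.** Reconcile Protocol 7.5.1, 7.5.2, 8.6.6, 8.6.9 and 8.7, leaving the pausing and stopping thresholds as they are:

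1. In 8.6.6 and 8.7, put the events already listed in 7.5.1 and 7.5.2 on the protocol's existing 24-hour EDC route to the sponsor.
2. Keep the 10-working-day line for submissions to the IRB and FDA.
3. Make the SAE entry in 8.7 agree with 8.6.6.
4. State in 8.6.6 whether completion of the study is per subject or per trial, and add the sponsor as a recipient of suspected related SAEs learned of afterwards.

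While these sections are open, correct the cross-reference in 7.1.1, which points to 8.5 for the pausing and stopping rules although they stand in 7.5.

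The cost is protocol wording, an EDC alert and a small added reporting load at sites. Protocol 4.3 describes device-related TEAEs in earlier trials as very infrequent and mild, so few extra reports should be expected.
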